4.5 Exposure

The exposure to trial medication (dasiglucagon or GlucaGen) for evaluation of pharmacokinetics will be assessed based on plasma concentration data from samples collected at the dosing visit (Visit 2):

CONFIDENTIAL

Sponsor:	Zealand Pharma A/S	Protocol Number:	ZP4207-16137
----------	--------------------	------------------	--------------

- Area under the drug concentration curve from time zero to 90 minutes, $AUC_{0-90\text{ min}}$.
- Maximum plasma drug concentration (C_{\max}).
- Time to maximum plasma drug concentration (t_{\max}).

Samples (including back-up samples) will be collected pre-dose, and at 15, 30, 35, 40, 50, 60, 90, and 120 minutes after dosing. The actual time of blood sampling for exposure to trial medication should not deviate from the nominal time by more than ± 1 minute. Pre-dose is defined as within 2 minutes prior to dosing.

All data collected related to study drug administration will be provided in the data listings.

4.6 Prior and Concomitant Medication

Prior glucagon exposure will be recorded in the eCRF at screening. All concomitant medications will be recorded and/or updated in the eCRF at each visit, i.e., at screening (Visit 1), the dosing visit (Visit 2, prior to the start of the insulin-induced hypoglycemic procedure) and at the follow-up visit (Visit 3).

Subjects using any new concomitant medication resulting in fulfillment of a dosing day exclusion criterion (see Protocol Section 5.5 “Dosing Day Exclusion Criteria”) will be excluded from the dosing visit, but can be rescheduled to one of the following days (1–7 days later). The dosing visit can only be rescheduled once.

Prior and concomitant medications will be coded using the World Health Organization (WHO) Drug Dictionary, version 2017Dec.

Incidence of prior and concomitant medication will be presented by treatment, drug class, and preferred drug name using patients in the Safety analysis set.

Prior medications are those that started and stopped before exposure to study medication; concomitant medications are all medications taken during the study period, including those started before but ongoing at first dose of study drug.

Where a medication start date is partially or fully missing, and it is unclear as to whether the medication is prior or concomitant, it will be assumed that it is concomitant.

4.7 Efficacy / Primary and Secondary Analysis

For the confirmatory analyses, the primary and key secondary endpoints for the dasiglucagon 0.6 mg and placebo treated subjects will be compared. A hierarchical procedure will be applied for the control of multiplicity. The primary and secondary endpoints will be evaluated on the Full analysis set. In the primary analysis, recovery cannot be achieved in those subjects where IV glucose treatment is administered. Those subjects who receive IV glucose will be censored (i.e., set to ‘not recovered’) at 45 minutes after dosing. In sensitivity analyses, the time to plasma glucose recovery will be analyzed 1) without censoring for those subjects who require rescue IV

CONFIDENTIAL

Sponsor:	Zealand Pharma A/S	Protocol Number:	ZP4207-16137
----------	--------------------	------------------	--------------

glucose before 45 minutes and 2) with censoring at the time of administration of rescue IV glucose before 45 minutes.

4.7.1. Hierarchical testing procedure

For the confirmatory analyses, the following a priori defined hierarchical inferential test order will be applied for the control of the type 1 error rate across the planned multiple comparisons. The primary endpoint and key secondary endpoints will be inferentially evaluated within the Full analysis set in the following order, where inference will proceed at the two sided 0.05 criterion significance level until the first failure to reject the null hypothesis for a dasiglucagon versus placebo comparison:

- Primary: Time to plasma glucose recovery
- Key secondaries 1-4: Plasma glucose recovery within 30 minutes, within 20 minutes, within 15 minutes, and within 10 minutes after study drug injection without administration of rescue IV glucose.
- Key secondaries 5-8: Plasma glucose changes from baseline within 30 minutes, within 20 minutes, within 15 minutes, and within 10 minutes after study drug injection or at the time of rescue.

The GlucaGen versus placebo comparisons will not be included in the inferential testing hierarchy, since the efficacy of GlucaGen is previously established, and these comparisons are intended to support the validity of the study for the dasiglucagon versus placebo comparisons.

Analogous supportive sensitivity analyses will be conducted in the PP set, but without inference intent.

4.7.2. Primary endpoint

- Time to plasma glucose recovery. Plasma glucose recovery is defined as first increase in plasma glucose of ≥ 20 mg/dL (1.1 mmol/L) from baseline during the hypoglycemic clamp procedure without administration of rescue IV glucose.

The planned time points at 0, 6, 8, 10, 12, 15, 17, 20, 25, 30, 40, 50 and 60 minutes will be used in the analyses.

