 - Pre-dose, 4, 6, 8, 10, 12, 15, 17, 20, 25, 30, 40, 50, 60, 75, and 90 minutes after dosing. The actual time for blood sampling for plasma glucose should not deviate from the nominal time by more than ± 30 seconds until the 20 minute collection time point and by more than ± 1 minute for the subsequent collection time points. Pre-dose is defined as within 2 minutes prior to dosing.
- Antibodies against dasiglucagon/GlucaGen (prior to the start of the insulin-induced hypoglycemic procedure).
- Plasma insulin concentrations:
 - Pre-dose, 30 and 60 minutes after dosing. The actual time of blood sampling for plasma insulin should not deviate from the nominal time by more than ± 1 minute. Pre-dose is defined as within 2 minutes prior to dosing.

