3.9 Sample Size

Due to requirements in the size of the safety database, the sample size is set to 78 subjects treated with dasiglucagon 0.6 mg. From phase 2, the median time to an increase of 20 mg/dL of the 0.6 mg dose was approximately 10 minutes. With a 2:1:1 randomization ratio for the three treatments, dasiglucagon 0.6 mg, placebo, and GlucaGen 1 mg, and assuming an exponential time-to-recovery distributions with median times of 10 and at least 20 minutes for dasiglucagon and placebo, respectively, a two-sided log-rank test will be able to detect a difference between dasiglucagon and placebo with 90% power with a follow-up time of 45 minutes at a 5% significance level with 78 subjects treated with dasiglucagon and 39 subjects with placebo. The median time-to-recovery for placebo is expected to be longer than 20 minutes, which means that the power will be greater than 90%.

4 Statistical Methodology

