The primary endpoint will additionally be analyzed using a Cox proportional hazards (CPH) time to event statistical model, if the hazards by treatment group can be assumed proportional using a graphical comparison of log-minus-log survival curves and no more than two-thirds of the recovery times are censored in each treatment group. The CPH model will be used for descriptive purposes, with treatment group and injection site modeled as categorical effects, and baseline plasma glucose modelled as a continuous covariate. The treatment group rate ratios, active versus placebo, will be estimated together with the 95% confidence intervals, and pairwise treatment group inferences (dasiglucagon vs placebo, GlucaGen vs placebo) will be evaluated using two-sided likelihood ratio tests.

Due to the discrete nature of blood sampling in time, and the fact that there must be a true, but unmeasured, ordering of the recovery times, the method using the “exact discrete” partial likelihood for tied failure times will be applied. In SAS, this is implemented in the phreg procedure with the option ties=discrete. The influence of injection site on time to recovery will also be evaluated in the proportional hazards model by a ‘type 3’ test in the phreg procedure.

To obtain an estimate of these true, but unassessed, patient recovery times, a linear interpolation (between the two time points before and after recovery is observed) will be carried out to estimate the patients’ actual time of recovery. These derived recovery times will be described and analysed in the same manner as for the discrete times above.

CONFIDENTIAL

Sponsor:	Zealand Pharma A/S	Protocol Number:	ZP4207-16137
----------	--------------------	------------------	--------------

Table 4-1: Definition of Events, Censoring, and Populations for Time to Event Analyses

Time to Event Endpoint	Initiating Event	Terminating Event(s)	Censoring Event(s) /Competing Risk(s)	Analysis Sample	Study Endpoint /Statistical Analyses
Time to plasma glucose recovery	Administration of IMP	First increase in plasma glucose of ≥ 20 mg/dL (1.1 mmol/L) from baseline w/out rescue IV glucose admin.	Rescue IV glucose administration will be censored at 45 minutes after IMP dosing	Full analysis set, PP	Primary/ Pairwise two-sided log rank test

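### The primary-endpoint time points leave out the scheduled 4-minute glucose sample without a reason, which shifts some early recovery times but hardly touches the primary test

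*SAP*

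**What the plan says.** Section 3.3.2 (dosing visit) gives the plasma glucose schedule as "Pre-dose, 4, 6, 8, 10, 12, 15, 17, 20, 25, 30, 40, 50, 60, 75, and 90 minutes after dosing", with a tolerance of 30 seconds either way up to the 20-minute sample.

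Section 4.7.2 (primary endpoint) defines the event: "Plasma glucose recovery is defined as first increase in plasma glucose of ≥ 20 mg/dL (1.1 mmol/L) from baseline", without rescue IV glucose. It then fixes the sampling times for the analysis: "The planned time points at 0, 6, 8, 10, 12, 15, 17, 20, 25, 30, 40, 50 and 60 minutes will be used". The 4-minute sample is not among them and no reason is given. The 75- and 90-minute samples are also left out, but they lie beyond the 45-minute follow-up used in sections 3.9 and 4.12. The 4-minute sample is the only scheduled one inside that follow-up that is dropped.

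Section 4.7.2.1 analyses recovery in two ways. The confirmatory test is a log-rank test, stratified by injection site, on recovery dated to the sampling times. In addition, "a linear interpolation (between the two time points before and after recovery is observed) will be carried out" to estimate each subject's actual recovery time, and the derived times are described and analysed in the same manner. The section also plans a histogram of recoveries by time interval for each group.

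**The concern.** The event definition and the time-point list disagree. By the definition, a rise of 20 mg/dL seen at 4 minutes is the event. By the list, that value is not looked at. Two programmers, one working from the definition and one from the list, could build different primary datasets.

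Following the list has two consequences:

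- **Discrete times.** A subject recovered at 4 minutes is dated to 6 minutes, or later if the 6-minute value has fallen back below the cut-off.
- **Interpolated times.** For a subject first recovered at 6 minutes, the earlier point of the bracket becomes 0 instead of 4. This applies even if nobody has recovered by 4 minutes.

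At stake are the accuracy and reproducibility of the earliest recovery times, in a trial whose primary endpoint is time to recovery and whose expected median on dasiglucagon is about 10 minutes.

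**Working it through.** **Inputs.** Section 3.9: 78 dasiglucagon and 39 placebo subjects; "assuming an exponential time-to-recovery distributions with median times of 10 and at least 20 minutes for dasiglucagon and placebo, respectively"; a two-sided log-rank test "with 90% power with a follow-up time of 45 minutes at a 5% significance level". Sampling times are from sections 3.3.2 and 4.7.2, and the interpolation rule from section 4.7.2.1.

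**1. The plan's own power.**
- Expected events by 45 minutes: 78 × (1 − 2^(−45/10)) + 39 × (1 − 2^(−45/20)) = 78 × 0.956 + 39 × 0.790 = 105.4.
- With hazard ratio 2 and 2:1 allocation, Schoenfeld's formula gives 91.8% (99 events are needed for 90%).
- A Wald test on the log hazard gives 89.9%.
- A continuous-time log-rank simulation (4,000 trials) gives 90.4%.

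The stated 90% is reproduced.

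**2. Effect on the test and the median.** The same simulated trials were dated to the sampling grid, using an unstratified log-rank test:

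| | With 4 min | Without 4 min |
|---|---|---|
| Power | 89.5% | 89.4% |
| Mean of the dasiglucagon median | 11.2 min | 11.2 min |

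The mean absolute shift in the z statistic is about 0.03.

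**3. How many subjects could be dated late in the discrete analysis.**
- Exponential, median 10: 1 − 2^(−4/10) = 24.2%; × 78 = 18.9, about 19 subjects.
- Exponential, median 20: 1 − 2^(−4/20) = 12.9%; × 39 = 5.0, about 5 subjects.
- Assumed lognormal, median 10, standard deviation of the log 0.3 to 0.6 (few very early recoveries): Φ(ln 0.4 / 0.3) = 0.1% to Φ(ln 0.4 / 0.6) = 6.3%; × 78 = 0 to 5 subjects.

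The SAP gives no observed early-recovery rate, so the range stays open.

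**4. Interpolated times for a recovery first seen at 6 minutes.** Let y4 and y6 be the rises from baseline at 4 and 6 minutes, with y4 < 20 ≤ y6.
- With the sample: 4 + 2 × (20 − y4)/(y6 − y4).
- Without it: 6 × 20/y6.

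| y4, y6 (illustrative, mg/dL) | With 4 min | Without 4 min |
|---|---|---|
| 0, 40 | 4 + 2 × 20/40 = 5.0 | 120/40 = 3.0 |
| 5, 30 | 4 + 2 × 15/25 = 5.2 | 120/30 = 4.0 |
| 10, 25 | 4 + 2 × 10/15 = 5.3 | 120/25 = 4.8 |

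Both lines end at the 6-minute value. The 0–6 line therefore crosses 20 earlier exactly when y4 lies below it, that is when y4 < (4/6) × y6, the slow-start case. If y4 lies above that line, the error goes the other way.

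**5. Key secondary endpoints.** The binary cut-offs are 10, 15, 20 and 30 minutes. A subject recovered at 4 minutes and still recovered at 6 to 10 minutes is counted in all of them on either list. Only a rise that does not persist could change the count.

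**The case against.** The strongest case against is that this is a minor mismatch between two lists. The confirmatory log-rank test is barely affected, the key secondary cut-offs come later, and the interpolated times are a supplementary analysis. The profiles in the table above are invented. The omission may be deliberate: the protocol is not shown, and section 4.14 says the planned analyses have not changed from it. All of this stands as a limit on the size of the point. It does not remove the unexplained conflict between the list and the first-increase definition.

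Four stronger readings are tempting but not supported:

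- **That about a quarter of the dasiglucagon arm will be misdated.** The figure of 19 of 78 needs an exponential hazard at full strength from the moment of injection. Section 3.9 uses that distribution for sample size, not to describe early glucose kinetics.
- **That both errors occur at full size.** Late dating needs many recoveries by 4 minutes, whereas the early interpolation error needs a slow start. The more of one, the less of the other.
- **That the comparison is weakened or tilted towards the product.** Power and median are practically unchanged. Under the exponential model more dasiglucagon than placebo subjects are dated late (24.2% against 12.9%), which does not favour dasiglucagon. The extra ties amount to one tied group that could have been two.
- **That the glucose AUC over 0 to 30 minutes also loses the sample.** Section 4.7.4.1 sets only the time window for the AUC. The restricted list stands under the primary endpoint.

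**Conclusion.** The point holds as one of consistency and precision. Section 4.7.2 drops a scheduled sample from within the follow-up without a reason, against its own definition of the event.

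- In the discrete analysis, recoveries already present at 4 minutes are dated 2 minutes late, or later still if the rise is lost by 6 minutes. The number affected is unknown: about 19 of 78 dasiglucagon subjects under the exponential assumption, 0 to 5 under the assumed lognormal.
- In the interpolated analysis, recoveries first seen at 6 minutes are dated too early if glucose rises slowly at first, by about 0.5 to 2 minutes in the illustrative profiles.

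The effect on log-rank power and on the median is negligible. The simulation behind that statement is unstratified, whereas the planned test is stratified by injection site, and it rests on the SAP's exponential medians of 10 and 20 minutes. The trial's main conclusion is not in question.

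**What to change.** Insert 4 minutes between 0 and 6 in the section 4.7.2 list, and state that the list applies to the discrete primary analysis, the interpolated recovery times and the recovery histogram. Do this before unblinding, since deciding later whether a collected value counts towards the primary endpoint would be a post-hoc choice. If the omission is deliberate, reconcile sections 3.3.2 and 4.7.2 and give the reason in one sentence. No change is needed for the glucose AUC.

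The cost is one number, or one sentence. The sample is already in the schedule, so no new data are required. If the protocol carries the same restricted list, the change must also be recorded and justified as section 4.14 requires.

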4.12 Subject Withdrawals and Missing Data

Failure is defined for the primary time-to-recovery endpoint as censored with time to recovery set to the maximum follow-up time, here 45 minutes. Individuals will be set to 'failure' in case of receiving rescue IV glucose, discontinuation due to treatment or discontinuation in connection with the induced hypoglycemia state. Only if an intermediate assessment is missing independent of rescue treatment, study treatment or an adverse event including hypoglycemia, a linear interpolation can be applied to impute a missing value.

The same construct of imputation for missing values applies for the analysis of the plasma glucose AUC0-30min.

In the case of subject withdrawal, no imputation of values for PK or PD measurements will be done. Analyses will be done on valid cases only, i.e., no imputation techniques such as last observation carried forward will be applied.

CONFIDENTIAL

Sponsor:	Zealand Pharma A/S	Protocol Number:	ZP4207-16137
----------	--------------------	------------------	--------------

Methods for Handling Missing Dates

All analyses and descriptive summaries will be based on the observed data. For the subject data listings, no imputation of incomplete dates will be applied. The listings will present the incomplete dates without any change.

Missing or Partial Death Dates

- If the entire date is missing, the death date will be imputed as the day after the date of last contact.
- If the day or both day and month is missing, the death date will be imputed to the maximum of the full (non-imputed) day after the date of last contact and the following:
 - If day is missing, day will be 1st of the month
 - If both day and month are missing, death month and day will be January 1st.

Missing Dates in Adverse Events/Concomitant Therapies

Dates missing the day or both the day and month of the year will adhere to the following conventions:

- The missing day of onset of an AE or start date of a therapy will be set to:
 - first day of the month that the event occurred, if the onset yyyy-mm is after the yyyy-mm of first study treatment
 - the day of the first study treatment, if the onset yyyy-mm is the same as yyyy-mm of the first study treatment
 - the date of informed consent, if the onset yyyy-mm is before the yyyy-mm of the first treatment
- The missing day of resolution of an AE or end date of a therapy will be set to:

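### The SAP gives two incompatible horizons for the primary endpoint (45 and 60 minutes) and no rule for censoring subjects who are neither recovered nor rescued at 45 minutes

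*SAP*

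**What the plan says.** **Pointing to 45 minutes.**
- Section 3.9 powers the log-rank test "with a follow-up time of 45 minutes".
- Section 4.12: "Failure is defined for the primary time-to-recovery endpoint as censored with time to recovery set to the maximum follow-up time, here 45 minutes". It then names who is set to failure: subjects given rescue IV glucose, and subjects who discontinue because of treatment or in connection with the induced hypoglycemia.
- Table 4-1 in section 4.7.2.1: "Rescue IV glucose administration will be censored at 45 minutes after IMP dosing". Sections 4.7 and 4.7.2.1 say the same in their text.

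**Pointing to 60 minutes.**
- Section 4.7.2, under the primary endpoint: "The planned time points at 0, 6, 8, 10, 12, 15, 17, 20, 25, 30, 40, 50 and 60 minutes will be used".

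**Not stated.** No sentence censors a subject at 45 minutes who has neither recovered, nor been rescued, nor discontinued. For the secondary endpoint of time to 70 mg/dL, section 4.7.4.1 does have such a rule: anyone who has not met it within 45 minutes is censored at the last valid measurement up to 45 minutes.

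**Sampling.** Section 3.3.2 collects plasma glucose at "Pre-dose, 4, 6, 8, 10, 12, 15, 17, 20, 25, 30, 40, 50, 60, 75, and 90 minutes after dosing". There is no 45-minute sample, and the 4-minute sample is absent from the list in section 4.7.2.

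**The concern.** Section 4.7.2.1 intends that a rescued subject cannot recover. Censoring at 45 minutes expresses this only if nobody can have an event later. If recoveries at 50 and 60 minutes are events, rescued subjects drop out of the risk set just before them. The curve after 45 minutes then rests on subjects who avoided rescue, and their recovery rate is credited to those who needed it. That is informative censoring.

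Time to recovery is the first test in the hierarchy of section 4.7.1. Two programmers following this text could produce different event counts, late curves, medians and p-values. They could also disagree on whether the Cox model is run, because section 4.7.2.1 requires that no more than two-thirds of times be censored in each group. Neither planned rescue sensitivity analysis varies the horizon. If the choice is made after unblinding, it becomes a data-dependent choice in the primary analysis.

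**Working it through.** **1. The plan's own power figure.** Inputs from section 3.9: 78 and 39 subjects, two-sided 5%, exponential times with medians of 10 and 20 minutes (hazard ratio 2), follow-up 45 minutes.

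Expected events = 78 × (1 − 2^(−45/10)) + 39 × (1 − 2^(−45/20)) = 74.6 + 30.8 = 105.4.

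Schoenfeld power = Φ(√(105.4 × 2/3 × 1/3) × ln 2 − 1.96) = Φ(1.39) = 91.8%, close to the stated 90%.

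The same formula gives 102.4 events and 91.1% if 40 minutes is the last usable sample, and 110.9 events and 93.1% at 60 minutes. The stated power fits a 45-minute horizon slightly better, but the differences are too small to settle which horizon was meant.

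**2. How the bias arises.** If 50- and 60-minute recoveries count, then S(60) = S(40) × (share of the unrescued, unrecovered subjects who stay unrecovered to 60). If rescued subjects stay at risk as failures, S(60) is the plain proportion not recovered without rescue.

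**3. Size under assumed placebo counts (n = 39).** The SAP gives no rescue or late-recovery rates, so every count here is an assumption.

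*Moderate case.* Exponential recovery with a 60-minute median, 10 rescued among those unrecovered at 40 minutes.
- S(40) = 2^(−40/60) = 0.630, or 24.6 subjects. Of these, 14.6 are unrescued.
- Conditional recovery from 40 to 60 minutes = 1 − 2^(−20/60) = 21%.
- Rescued censored at 45: S(60) = 0.630 × 0.794 = 0.50.
- Rescued kept as failures: S(60) = (10 + 14.6 × 0.794)/39 = 0.55.

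*Extreme case.* 12 recover by 40 minutes, 10 are rescued, 6 recover at 50, 5 at 60, and 6 never do.
- Rescued censored at 45: S(50) = 27/39 × 11/17 = 0.448; S(60) = 0.448 × 6/11 = 0.244; median 50 minutes.
- Rescued kept as failures: S(50) = 21/39 = 0.538; S(60) = 16/39 = 0.410; median 60 minutes.
- Cox condition: a 45-minute horizon censors 27/39 = 69% of placebo, so the model is not run. Counting 50 and 60 censors 16/39 = 41%, so that condition is met.

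**4. Effect on the log-rank test.** Simulation on the SAP's sampling grid, unstratified, 1,500 runs, dasiglucagon median 10 minutes. A given share of subjects in either arm not recovered by 30 minutes is rescued (assumed).

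| Placebo median, share rescued | Power: rescued censored at 45, late events count | Power: everyone cut at 45 | Power: rescued held to 60 | Placebo recovery at 60: first rule vs actual |
|---|---|---|---|---|
| 20 min, 0% | 91.5% | 89.3% | 91.5% | 87.6% vs 87.6% |
| 20 min, 25% | 90.5% | 88.3% | 88.9% | 86.2% vs 81.9% |
| 20 min, 50% | 89.0% | 87.5% | 87.4% | 84.7% vs 75.9% |
| 60 min, 50% | about 100% | about 100% | about 100% | 47.0% vs 39.6% |

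The Monte Carlo standard error of a power near 89% is √(0.89 × 0.11/1500) = 0.8 points.

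**The case against.** The strongest reply is that section 4.12 calls 45 minutes the maximum follow-up for this endpoint and section 3.9 powers the test on it. On that reading no recovery at 50 or 60 minutes enters and no bias arises. The time-point list may also have a harmless purpose. Section 4.7.2.1 interpolates recovery times between the samples on either side of the crossing, and a crossing between 40 and 45 minutes needs the 50-minute value. This stands. A reader might infer that late recoveries definitely count and that the primary analysis is therefore biased; the documents leave that open. It also means that simply deleting 50 and 60 minutes would remove data a planned step needs. The reply does not supply the missing censoring rule, which section 4.7.4.1 shows the authors knew how to write.

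A second reply is that the harm is small, and this largely stands. The extreme case has 11 of 17 unrescued subjects recovering in 20 minutes after only 12 of 39 did so in the first 40; nothing in the SAP supports such a surge. With the SAP's 20-minute placebo median, the curve crosses one half well before 45 minutes, so the median is unlikely to move.

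Third, if rescue falls mostly on placebo, the late placebo curve errs against dasiglucagon. That rescue pattern is plausible but not stated. I would not rely on the error being conservative for the test: with equal rescue shares among those unrecovered at 30 minutes, simulated power was marginally higher under the mixed rule, not lower.

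**Conclusion.** The point holds as an unresolved contradiction. Sections 3.9 and 4.12 give a 45-minute horizon, section 4.7.2 lists samples to 60 minutes, and no rule covers the unrescued, unrecovered subject at 45 minutes. Bias follows on only one of the two readings. On that reading it is confined to the Kaplan-Meier curve after 45 minutes and quantities read from it, in whichever arm has more rescue. Under the assumptions tried, the gap at 60 minutes runs from about 5 points (moderate case) to 17 points (extreme case), and is zero without rescue.

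The effect on the log-rank test is probably small. Estimates up to 40 minutes and the key secondary endpoints at 10 to 30 minutes do not change. A reader might infer that the confirmatory conclusion is in danger; neither the SAP nor these calculations support that. The case for acting is that the primary analysis should have a single reading before unblinding. The omitted 4-minute sample is a separate, minor matter: a recovery at 4 minutes would be dated 6 minutes.

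**What to change.** Before unblinding, state one horizon for all subjects in section 4.7.2, Table 4-1 and section 4.12, after checking it against the protocol. Two versions are coherent:

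1. **45 minutes, which agrees with sections 3.9 and 4.12.** Every subject not recovered by 45 minutes is censored at 45 minutes, whatever the reason. The last nominal sample that can record an event is then 40 minutes. The 50-minute sample serves only to interpolate crossings before 45 minutes. Cost: recoveries first seen at 50 or 60 minutes no longer count, apart from interpolated crossings before 45 minutes in the interpolation analysis.
2. **60 minutes.** Recoveries at 50 and 60 minutes are events, and rescued and discontinued subjects are held as not recovered through that same time. Cost: sections 3.9 and 4.12 and every 45-minute censoring statement for this endpoint must change to match.

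In either case, say that the two-thirds censoring condition for the Cox model is judged on the chosen horizon, and how interpolated times near its end are treated. Add the collected 4-minute sample to the list in section 4.7.2. The work is a few sentences and a small programming rule; no new data are needed.
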